3.0 PATIENTS

3.1 Trial Entry

Women undergoing ANC will be monitored from pre-surgery baseline, with perometer measurements and BEA (please note, only the initial 1100 recruits will have BEA measurements) to compare the sensitivity and specificity of both techniques for predicting chronic lymphoedema development. Identifying the most sensitive and specific method for detecting chronic lymphoedema would enhance selection of patients for intervention with arm sleeves should the intervention prove cost effective.

Approximately 1400 patients will be enrolled over a 5 year period over 9 investigative sites; North Manchester, South Manchester, London, Derby, North Staffordshire, Poole, Bournemouth and Wolverhampton.

Patients will be registered by a telephone call to the MAHSC Clinical Trials Co-ordination Unit ([name]).

3.2 Inclusion Criteria

- Women aged 18-90 years.
- Early breast cancer (no evidence of metastatic disease by local screening procedures), scheduled to undergo axillary node clearance.
- Willing to consent to pre-surgical arm measurements by perometry and BEA.
- Agreeable to follow-up for up to five years.
- Written informed consent to enter bioimpedance study.

3.3 Exclusion Criteria

- Any patients unwilling to consent to pre-surgical baseline measurements.
- Known distant metastasis.
- Inoperable breast cancer (T4 category or distant metastasis).
- Node negative not undergoing axillary clearance.
- Previous axillary radiotherapy or clearance.
- Past history of breast/chest wall radiotherapy.
- Previous axillary clearance; either unilateral or bilateral.
- Pregnancy.
- External pacemaker/defibrillator.

3.4 Treatment Measurements

For the first 1100 recruits (recruited before January 2015), arm volume will be measured at baseline, 1, 3, 6, 9 and 12 months then 6 monthly thereafter to 2 years, followed by annual measurements to 5 years using perometer arm scanning (and circumferential tape measurement of arm girth with anatomic landmarks (e.g. lateral epicondyle) as reference points). The contralateral arm will act as a control. *For the additional 300 patients (recruited from February 2015, on version 3.1 or higher of the patient information leaflet), these measurements will take place at baseline, 1, 3, 6, and 9 months only.*

Patients developing a 4-8.9% increase in arm volume within 9 months of arm surgery will be offered randomisation. Within the same visit, patients will undergo multi-frequency bioimpedance measurements, comparing the affected arm with the contralateral arm and the leg. Bioimpedance measurements will not lead to change of treatment but will be recorded and performed according to the trial Standard Operating Procedures (please note, Bioimpedance will only be measured in

the 1100 patients who are part of the 5 year study. Subsequent patients, who will only be followed up for 9 months, will not undergo this assessment).

Perometer measurements demonstrating an increase in arm volume >10% (on two occasions) will be utilised to commence treatment for lymphoedema.

For the first 1100 participants, FACT B+4 questionnaires will be administered at all visits apart from the 1 month visit to permit calculation of Trial Outcome Index (FACT B TOD following the ATAC Trial methodology. ^[PG 60] A lymphoedema symptom questionnaire will be administered at the same time points. EQ5D questionnaires will be administered at all time points apart from months 3, 36, 48 and 60.

Please note, quality of life questionnaires will only be administered at baseline for the final 300 participants.

3.5 Sample Collection

A 20m1 PaxGene sample is to be collected on one occasion from all patients who have given their informed consent to provide blood samples. PaxGene, samples will be collected during any scheduled study visit as these samples are not time critical. The analysis of these blood samples has not yet been finalised, but we would like to perform some tests that will give us additional information on the effects of surgery and the effects of treatment following surgery on the lymphatic system. We are also interested in finding out through DNA and RNA analysis whether there are any genes that may cause lymphoedema after surgery, or increase the chance of side effects from radiotherapy.

Breast tumour specimens will be collected and, where patients have given their informed consent, these tissue samples may be used for future research.

3.6 Data Management

CRFs will be provided for recording of all data. Each one will be printed on a single sheet. Data will be recorded directly and legibly on the CRFs in black ballpoint pen. Entries should be made legibly and initialled and dated by approved personnel. The reasons for significant changes must be provided. Correction fluid or covering labels must not be used. The MAHSC Clinical Trials Co-ordination Unit (CTU), Manchester will provide data management for all centres and a copy of the CRF will be sent to the Data Manager at The MAHSC CTU in Manchester.

4 STUDY OBJECTIVES

4.2 Primary Objective

1) Incidence of lymphoedema at 2 and 5 years after axillary node clearance (*assessed by perometer scanning*).

4.3 Secondary Objectives

- 1) Comparison of multi-frequency BEA with perometer measurement.
- 2) Prediction of lymphoedema by multi-frequency BEA at 24 months.
- 3) Quality of life in each group (T01 and FACT B+4).
- 4) Multivariate model assessment of factors predicting lymphoedema at 24 months.
- 5) Lymphoedema symptoms related to changes in arm volume and bioimpedance readings.

5 STATISTICAL ANALYSIS

Analysis 1 and 2 will directly compare BEA and perometer assessment at a given time point (6 and 18 months). The reported concordance/correlation in small series is 0.93¹³⁴¹. Thus, even if a sleeve has been applied in patients before 6 months' measurements and the arm circumference has been reduced, the reduction in fluid in the arm should have reduced both the perometer and BEA scores concomitantly.

Sample Size Calculation

We estimate 1100 women are needed for screening by perometer to recruit 270 women to the PLACE trial and this sample size of 1100 (derived from having approached 1500 women to take part in the study) allows us to assess equivalence for sensitivity and specificity for BEA compared to perometer measurement with tight confidence intervals. Previous reported correlation between the techniques is very high¹¹⁵, and this sample size allows us to have a 95% Confidence Interval (CI) around our sensitivity and specificity estimates such that they are $\pm 5\%$ or less. Thus if perometer and BEA are equivalent in sensitivity and specificity to within 5% of each other, we would expect that the BEA would become the preferred option as it would be mobile, non-invasive and simpler to use in any outpatient setting compared to a fixed, large instrument, such as the perometer. There will be less patients with lymphoedema at 6 months but nonetheless if BEA sensitivity is 95% of the perometer sensitivity, we can demonstrate this with a 95% CI of 91.42% to 97.49%. If the BEA sensitivity rate was as low as 90%, we would have a 95% CI of 85.12% to 93.49%. All subsequent analyses will use sample sizes based on larger numbers as there will be more lymphoedema events at 18 months and again at 36 months but their confidence intervals are within $\pm 5\%$. We have used the exact method for calculating confidence intervals for a binomial proportion (Documenta Geigy Scientific tables page 185 equation 769); the actual calculation was done using the www.measuringusability.com/wald.htm website calculator.

The sample will allow us to measure accurately, inter- and intra-technique variability at different time points.

Analyses 1 to 3 will assess whether BEA can be used instead of perometer in defining lymphoedema status. The second group of analyses is to look for any variables collected at operation or in the first 6 months post operation that singly or in combination can be used to predict lymphoedema status at or beyond 18 months.

Analysis 1

Sensitivity and specificity analysis of the BEA assessment (lymphoedema or not) against the 'gold standard' perometer assessment (lymphoedema or not) using data available by 6 months.

Analysis 2

Analysis of the sensitivity and specificity of the 18 month BEA assessment status (lymphoedema or not) against the 'gold standard' 18 month perometer assessment status (lymphoedema or not) using all data available at 18 months.

Analysis 3

Assessment of the relationship between perometer measurement and BEA measurement.

Analysis 4

Cox regression multivariate analysis of the time to Lymphoedema (as defined by perometer) to find out which combination of variables gives the best prediction of this complication.

Analysis details:

Analysis 1: Sensitivity and specificity analysis of the BEA assessment (lymphoedema or not) against the 'gold standard' perometer assessment (lymphoedema or not) using data available by 6 months. Can BEA be used instead of perometer in predicting lymphoedema status?

All cases with a 6 month BEA and perometer measurement will be used. This is acceptable even if some cases are treated as what we are asking is do cases measured at the same time (and therefore under the same circumstances whatever they are) agree in their assessment of lymphoedema status.

The two methods will not agree on their actual scores as perometer measurements are in percentage differences and BEA measures are ratios. However we will assess the relationship between all the pairs of values using statistical techniques recommended by Bland and Altman for assessing agreement between methods of measurements with multiple observations per individual^{36,311} (see also analysis 3).

With 1100 cases consented to having measurements taken and followed-up, we would expect 231 to have developed lymphoedema (positive) using perometer assessment and 869 to be negative at 6 months. If we accept that BEA status has at least 95% sensitivity and 95% specificity against the perometer status then the 95% CI for sensitivity based on 231 cases is 91.42% to 97.49% and for specificity based on 869 cases is 93.31% to 96.47% (CI's calculated by 'exact' method). Consequently if sensitivity is <91 % or specificity is <93% we can conclude that the true BEA rates are not as high as 95%. This analysis can be done 6 months after the last case has their 6 months measurements taken. The perometer is deemed to be the gold standard.

A further assessment of the BEA value cut off level will be made to see if a change in the standard definition is worth recommending (ROC analysis). This will be done at 18m from the start of the study (using cases accrued in the first year) and repeated on the new cases post 1 year recruitment to see if a new cut off level works on the second data group. The final sensitivity and specificity analysis will take place 6 months after the last case is recruited.

Analysis 2: Analysis of the sensitivity and specificity of the 18 month BEA assessment status (lymphoedema or not) against the 'gold standard' 18 month perometer assessment status (lymphoedema or not) using all data available at 18 months.

This analysis uses all the data available at 18 months, following the same logic and procedures as Analysis 1. Assuming at least 1,000 women are followed-up to 18 months after surgery, there will be more lymphoedema cases, this is estimated to be 35% of the total group (i.e. 350 cases). The sensitivity calculations produce a 95% CI for a 95% BEA sensitivity rate (333/350) against the perometer status at 18 months of 92.34 to 97.15 (again using the 'exact' method). The other 650 cases are used for the specificity calculation, here the 95% CI for 95% BEA specificity (618/650) has a 95% CI of 93.12 to 96.61. Consequently if sensitivity is <92% or specificity is <93% we can conclude that the true BEA rates are not as high as 95%.

Analysis 3: Assessment of the relationship between perometer measurement and BEA measurement. Any changes will be measured by both systems at different time points (1m, 3m, 6m, 12m and 18m and later on out to 5 years) and all results will be used as the modelling will be based on the paired perometer and BEA values. This will be used to define the relationship between the two methods (we will use Bland-Altman methods^{136,371} at individual time points and generalized estimating equations (GEE) regression models across time points). The relationship established may lead to a clearer definition of 'true' lymphoedema status when using either system.

Analysis 4: Cox regression multivariate analysis of the time to Lymphoedema (as defined by perometer) to find out what combination of variables gives the best prediction of these events.

For this 'modelling' analysis we will use 'time to the first lymphoedema event per case' as the measure (cases not becoming lymphoedema will be censored at their last assessment time) and apply a Cox regression multivariate analysis to see what variables (if any) predict the long term outcome. The variables listed below are candidates. Concerns about the treatment paradox affecting this analysis will be dealt with by excluding cases who develop lymphoedema before 6 months and using a factor 'sleeve' v 'no sleeve' in the model to adjust for the cases treated in PLACE.

BMI, dominant limb, postoperative radiotherapy, previous sentinel node biopsy, cigarette smoking, weight gain, and age. As we will be measuring the patient's assessment of their own status using FACT-B and the Lymphoedema Symptom Checklist we will also use individual question responses and the overall scores for these questionnaires out to 6 months. The BEA values and perometer values are available at baseline, 3 months and 6 months. The 3 months and 6 months values will be used as distinct time points or as summary scores over the 3 measurements. It may well be possible to have a factor that represents 'early treatment' or 'lymphoedema status before 6 months', in which case all the information will be used. These variables will be assessed univariately and then as part of a multivariate model to see if any predict lymphoedema status by 18 months follow up.

As routine clinical data on lymphoedema status will be available in due course with 5 year follow up, a subsequent analysis will be possible to build a predictive model of outcomes up to 5 years.

This analysis will take place 18 months after the last case is entered. For the multivariate regression analyses, it is typically recommended that between 10 and 30 cases per variable are used. The higher number of cases per variable are required when the relationships are weaker. With approximately 1000 cases this should allow us to examine around 30 variables with at least sufficient power to pick up moderately weak relationships. See analysis 4 for the type of variables we will be assessing.

All percentages for the 3 groups (A-C) are estimated from ALMANAC Trial data (see Annex 4d). None of the analyses outlined will use cases where a treatment for lymphoedema has been given prior to 6 months as explained above. A "treatment paradox" will not affect analyses 1 to 3 and treatment will be a variable in analysis. Potentially, the predictive value of a measurement at 6 months by perometry of the arm may be altered by treatment when assessing lymphoedema at 18 or 36 months. We do not believe this will occur for the majority of patients but in any case we will take account of this in the Cox multivariate regression analysis based on perometer measurements at 18 and 36 months and by looking at variables which include treatment with a compression sleeve. As we indicated in the flow diagram of this study, 3 possibilities may arise:

- Group A: Women in whom the arm volume increase is less than 4% at all time points up to 6 months (approximately 33% of the population; 330 individuals). None of these patients will undergo treatment within the first 6 months and therefore the measurement at 6 months will not be subject to "treatment paradox" and should they subsequently develop lymphoedema before 18 months, they will be registered as having developed the lymphoedema event in a time-dependant manner for the multivariate analysis and subsequent treatment will not affect this analysis.
- Group B: Women who will have developed a 4-10% arm volume increase by 6 months (estimated as 46% of the total group; 460 patients). Around 135 women from this group (with a 4-8.9% volume increase) will go into the PLACE trial and have a sleeve applied and a similar number will go into the PLACE trial and will not have an arm sleeve applied.

Thus, in this group there will be 325 patients (460 minus 135) who are not treated until they develop lymphoedema and will not have a "treatment paradox" for the same reason as previously described. Out of the 135 cases allocated to the sleeve arm within the PLACE trial, who are chosen at random, we will use their data in a multivariate analysis as we will incorporate it as a factor, sleeve versus no sleeve in building the model.

- Group C: Women who develop greater than 10% arm swelling by 6 months (approximately 210 patients). Arm swelling of greater than 10% at 1 month will need confirmation but in current practice, we would review these patients at 3 months, before deciding to put on an arm sleeve as some women do observe amelioration of swelling over this period following the operation. Thus we will have 3 month perometer readings on all patients in this group to compare with 3 month BEA measurements. All other patients will provide 6 month perometer and BEA measurements and will therefore be eligible for the analysis of the prediction of arm swelling at 18 and 36 months. The data for patients who have undergone treatment before 6 months in this group will not be included in our multivariate analysis, although we expect few cases to be excluded in this way.

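### A confidence-interval half-width of 5 points is used as an equivalence margin, but with the perometer as reference the planned 95% for BEA sits exactly on that margin

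*Protocol*

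**What the plan says.** All of this is in Protocol section 5.

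- **Claim.** The Sample Size Calculation says "this sample size of 1100 (derived from having approached 1500 women to take part in the study) allows us to assess equivalence for sensitivity" as well as specificity. After noting that the confidence intervals will be 5 points or less either side, it continues "Thus if perometer and BEA are equivalent in sensitivity and specificity to within 5% of each other", and expects that BEA would then be the preferred method.
- **Illustration.** "if BEA sensitivity is 95% of the perometer sensitivity, we can demonstrate this with a 95% CI of 91.42% to 97.49"; and "If the BEA sensitivity rate was as low as 90%, we would have a 95% CI of 85.12% to 93.49" (both in per cent).
- **Reference.** Under Analysis 1, "The perometer is deemed to be the gold standard". Analysis 2 follows the same logic at 18 months.
- **Numbers.** At 6 months "we would expect 231 to have developed lymphoedema (positive) using perometer assessment and 869 to be negative at 6 months", with an assumed 95% for both measures. The interval "for specificity based on 869 cases is 93.31% to 96.47% (CI's calculated by 'exact' method". At 18 months the counts are 333/350 (92.34 to 97.15) and 618/650 (93.12 to 96.61).
- **Thresholds.** If sensitivity is below 91% or specificity below 93% at 6 months (92% and 93% at 18 months), "we can conclude that the true BEA rates are not as high as 95" per cent.

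**The concern.** A narrow interval and a demonstration of equivalence are different things. Precision fixes how wide the interval is. Equivalence requires the whole interval to lie on the right side of the margin, so it also depends on where the true value lies relative to that margin. The protocol moves from the first to the second in consecutive sentences.

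A test used as the reference has sensitivity and specificity of 100% against itself. A gap of no more than 5 points, or BEA at 95% of the perometer's value, therefore both reduce to BEA of at least 95%. Planning for 95% places the assumed truth on the boundary.

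What is at stake is the conclusion on replacing the perometer with BEA. That comparison is the protocol's stated aim and its first secondary objective. A reader could take an estimate near 95% that crosses no threshold as the promised equivalence.

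**Working it through.** **Inputs (Protocol section 5).** 6 months: 231 perometer-positive, 869 negative. 18 months: 350 positive, 650 negative. Planned BEA rate 95%. Two-sided exact 95% intervals.

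**Step 1. Reproduce the stated intervals.** Exact (Clopper-Pearson) limits for x of n: lower = Beta quantile 0.025 with parameters (x, n−x+1); upper = Beta quantile 0.975 with parameters (x+1, n−x).

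| Quantity | Count | Recomputed | Stated |
|---|---|---|---|
| 6-month sensitivity, 95% | 219/231 | 91.10–97.29 | 91.42–97.49 |
| | 220/231 | 91.64–97.60 | |
| 6-month sensitivity, 90% | 208/231 | 85.44–93.58 | 85.12–93.49 |
| 6-month specificity, 95% | 826/869 | 93.39–96.40 | 93.31–96.47 |
| 18-month sensitivity | 333/350 | 92.34–97.15 | 92.34–97.15 |
| 18-month specificity | 618/650 | 93.12–96.61 | 93.12–96.61 |

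The 18-month figures match exactly and the 6-month figures to about 0.3 point. The widest distance from estimate to limit is 90 − 85.12 = 4.88 points, so the precision statement holds.

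**Step 2. Set the intervals against the margin.** Boundary = 100 − 5 = 95%. The four planned lower limits fall short of it by 95 − 91.42 = 3.58, 95 − 93.31 = 1.69, 95 − 92.34 = 2.66 and 95 − 93.12 = 1.88 points. In the 90% scenario the whole interval (85.12 to 93.49) lies below 95%.

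**Step 3. What equivalence would need.** Find the smallest count m whose exact lower limit exceeds 95%. Power = P(X ≥ m), with X binomial (n, true rate).

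| | m/n | Power at true 95% | 97% | 98% | True rate for 80% power |
|---|---|---|---|---|---|
| 6-month sensitivity | 226/231 | 2.4% | 30.6% | 68.3% | about 98.3% |
| 6-month specificity | 839/869 | 1.8% | 81.3% | 99.8% | about 97.0% |
| 18-month sensitivity | 341/350 | 1.8% | 39.4% | 83.3% | about 97.9% |
| 18-month specificity | 629/650 | 1.9% | 68.7% | 98.7% | about 97.2% |

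For example, 225/231 gives a lower limit of 94.43% and 226/231 gives 95.02%, so at most 5 of 231 positives may be missed.

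**Step 4. What the thresholds can show.** The 6-month sensitivity threshold is not crossed when at least 211 of 231 are detected (0.91 × 231 = 210.2). With a true sensitivity of 93%, outside the 5-point margin, P(X ≥ 211) = 86.7%. At 18 months, the corresponding figure for at least 322 of 350 (0.92 × 350 = 322) is 80.2%.

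**The case against.** Five points can be made for the plan.

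1. *The 2% figures are inherent.* A valid test at one-sided 2.5%, evaluated on its own boundary, passes no more than 2.5% of the time at any sample size. That is correct, and it means the fault lies in the planning value rather than in the number 1100. It would be too strong to infer that 1100 women could never show equivalence: with a true rate of 98%, Step 3 gives 68% to over 99%. Analysis 1 does speak of at least 95%, and section 1.5 cites 98% sensitivity and 100% specificity from small single-centre studies. Those figures concern earlier prediction of lymphoedema, and the sample-size section does not use them. Its only alternative scenario is lower, at 90%.

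2. *The thresholds are valid as worded.* This stands. They support a one-directional conclusion and nothing more. A reader might infer that BEA is to be accepted whenever it is not rejected. The protocol states no such rule, and the remark about a preferred option is conditional on equivalence. What remains is that no criterion says when equivalence has been shown.

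3. *The perometer has its own accuracy elsewhere.* Section 2.0 (Trial Design) gives it 85% sensitivity and 55% specificity, and sets a benchmark above 80% for BEA. That text concerns prediction of 18-month lymphoedema, where a 5-point difference is meaningful. The intervals in the Sample Size Calculation are those of Analysis 1, with the perometer as reference, so section 2.0 does not rescue them.

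4. *It is secondary.* BEA against perometer is a secondary objective, the 1100 also follows from recruitment to PLACE, and section 7 leaves treatment decisions with the perometer. This limits the consequences but does not remove the conflict.

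5. *The SAP may set the criterion.* It may, but the reference, margin, planning value and thresholds are fixed in the protocol and conflict there.

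**Conclusion.** The point holds in a bounded form. The precision claim is right. The claim that this size allows equivalence within 5 points to be shown is not supported at the protocol's own planning value: the probability is 1.8% to 2.4% for each of the four measures. About 80% power at 6 months needs a true sensitivity near 98.3% and a true specificity near 97%, neither of which is assumed. Staying above the thresholds is not evidence of equivalence, since a true 6-month sensitivity of 93% does so about 87% of the time.

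The documents do not support saying that the protocol adopts BEA by default, or that equivalence is out of reach whatever BEA's true accuracy.

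The figures assume the planned counts with no missing pairs at 6 months, a two-sided exact 95% interval, and each measure taken alone. The 87% refers to the sensitivity threshold only; a low specificity could also trigger the protocol's conclusion.

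**What to change.** In the Sample Size Calculation and Analyses 1 and 2:

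- Delete the claim of equivalence within 5%. State instead that the sample gives 95% intervals of about 5 points or less either side of the estimates.
- Add that not crossing the 91%/93% or 92%/93% thresholds does not establish equivalence.
- If an equivalence claim is to be kept, give the criterion (exact lower 95% limit above a bar that the sponsor justifies), the assumed true BEA value above that bar, and the resulting power.
- Keep a 5-point difference margin only for the comparison in section 2.0, where 6-month readings predict 18-month lymphoedema and the perometer has its own estimated accuracy.

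The first two changes and the last are wording only. The cost is a less favourable stated claim for BEA. Keeping an equivalence claim costs more, because the sponsor must defend a bar and a true value that the protocol does not now contain.

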2.0 TRIAL DESIGN

1100 women undergoing ANC for breast cancer in 9 centres across the UK will be approached to undergo baseline (pre-operative) and subsequent BEA monitoring, along with perometer arm measurements (see flow diagram). A comparison of the sensitivity and specificity of BEA versus perometer measurement will be made firstly in women who develop arm swelling >10% by 6 months (estimated at 231/1100 (21%) of the initial group). Percentages are estimated from ALMANAC Trial (see Annex 4d). Secondly women with an arm volume increase 4-8.9% at 1, 3, 6 months where effectively the BEA 6 months readings will be compared with final 18 month perometer scores to assess the prediction of lymphoedema at 18 months by BEA. Thirdly, women with a <4% Perometer arm volume increase up to 6 months (estimated n=363/1100 with estimated lymphoedema at 18 months of 46 (14% of 264)) will be used to determine the sensitivity and

specificity of BEA 6 month measures compared to the perometer 6 month measurement in predicting the 18 month outcome.

We originally estimated we would need to screen over 1000 patients to enrol sufficient women into the PLACE Trial using perometer measurements, we will determine if BEA has a >80% sensitive and a >80% specific accuracy and currently the specificity of arm swelling measured by perometer is 87% specific for subsequent lymphoedema at 18 months with a sensitivity of 54% (assessed from ALMANAC trial data). We will recruit 1100 women before ANC into the five year study to allow for 10% drop-out over the course of the study.

The Perometer sensitivity is reported as 85% +/-3.6% (95% CI 81.4% to 88.6%) and we will be able to detect a greater or equal to 7% improvement in sensitivity with BEA to 92+/-2.5% (95%CI: 89.5-94.5%) and the Perometer specificity is 55% +1-4.1% (95% CI 50.9% to 59.1%) thus we will be able to detect a >9% improvement in specificity with BEA to 64%+/-3.9% (95%CI:60.1 to 67.9%) with this sample size, since the confidence intervals do not overlap.

Gold standard at 18 months	Test P+	Test P-	Total
	+168[contact]
	-168[contact]
Total	336[contact]

sensitivity = 307/352 = 87%
 specificity = 284/523 = 54%

Arm volume measurement at 1 month will not be used to implement treatment outside of the trial. In women who develop lymphoedema >10% at 3 months, sleeves will be applied and the 3 month BEA value compared to the perometer used in the analysis. For all others, the 6 month value will be used.

[figure not shown]

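### The protocol's claim that all later analyses rest on larger numbers with intervals within ±5% is false for the 18-month prediction comparison in women with under 4% swelling, where it expects only 46 events

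*Protocol*

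**What the plan says.** Protocol Section 5, Sample Size Calculation, makes a general promise: "this sample size allows us to have a 95% Confidence Interval (CI) around our sensitivity and specificity estimates such that they are" ±5% or less. It illustrates this for the 6-month analysis at 95% and 90% sensitivity. It then says "All subsequent analyses will use sample sizes based on larger numbers as there will be more lymphoedema events at 18 months", and the sentence ends "and again at 36 months but their confidence intervals are within $\pm 5"%. The method is named: "We have used the exact method for calculating confidence intervals for a binomial proportion".

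Two whole-cohort tables are worked out. For Analysis 1, "we would expect 231 to have developed lymphoedema (positive) using perometer assessment and 869 to be negative at 6 months". For Analysis 2, the protocol assumes 350 cases among 1,000 women at 18 months.

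Section 2.0 plans more than these tables. After a first comparison in women already above 10% by 6 months, it sets 6-month BEA against 18-month perometer status in women with a 4-8.9% increase, and then separately in women below 4%. The last group is "estimated n=363/1100 with estimated lymphoedema at 18 months of 46" (given as 14% of 264). No event count is given for the 4-8.9% group. The same section states "we will determine if BEA has a >80% sensitive and a >80% specific accuracy".

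**The concern.** The sentence on larger numbers is universal, but its reason (more cumulative cases at 18 months) applies only when the whole cohort is in the table. The two prediction comparisons leave out women who already have lymphoedema by 6 months, so their sensitivity rests on new events alone. In the group below 4%, the protocol's own count is a fifth of the 6-month number (46/231 = 0.20).

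The trial's stated aim is to learn whether BEA identifies developing lymphoedema before perometry shows it, and only women not yet swollen can inform that. Someone relying on the sample-size text would expect these estimates to be good to ±5 points.

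**Working it through.** **1. The protocol's own intervals.** Exact (Clopper-Pearson) 95% limits for x of n are the 2.5% quantile of Beta(x, n−x+1) and the 97.5% quantile of Beta(x+1, n−x).
- Analysis 2: 333/350 gives 92.34-97.15 and 618/650 gives 93.12-96.61. Both match the protocol.
- Analysis 1, 231 cases at 95%: 219/231 gives 91.10-97.29 and 220/231 gives 91.64-97.60 (protocol 91.42-97.49).
- Analysis 1, 231 cases at 90%: 207/231 gives 84.94-93.23 and 208/231 gives 85.44-93.58 (protocol 85.12-93.49). Agreement is within about 0.3 point.

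So ±5 holds for both whole-cohort tables at the sensitivities illustrated. At 80% it holds for Analysis 2 (280/350: 75.4-84.1) but only just fails for Analysis 1 (185/231: 74.3-85.0, half-width 5.3).

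**2. Events in the prediction comparisons.**
- Below 4%: 46, stated. The bracketed basis does not fit: 0.14 × 264 = 37, 0.14 × 330 = 46, 0.14 × 363 = 51.
- New events per 1,000 women between 6 and 18 months: 350 − 210 (Group C in Section 5) = 140. With 1,100 as denominator: 0.35 × 1,100 − 231 = 154.
- Remainder for the 4-10% group: 140 − 46 = 94, or 154 − 46 = 108.

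The 140, 154, 94 and 108 are derived, not stated. They assume that every case by 6 months is still a case at 18 months.

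**3. Exact 95% intervals for sensitivity** (half-width = half the interval's length, in points).

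| Events | near 80% | near 90% | near 95% |
|---|---|---|---|
| 46 (stated, <4%) | 37/46: 66.1-90.6 (±12.3) | 41/46: 76.4-96.4 (±10.0) | 44/46: 85.2-99.5 (±7.2) |
| 94 (derived, 4-10%) | 75/94: 70.2-87.4 (±8.6) | 85/94: 82.6-95.5 (±6.5) | 89/94: 88.0-98.3 (±5.1) |
| 140 (derived, both) | 112/140: 72.4-86.3 (±6.9) | 126/140: 83.8-94.4 (±5.3) | 133/140: 90.0-98.0 (±4.0) |

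The intervals are asymmetric. At 44/46 the lower arm alone is 10.5 points. With 37 events in place of 46, 30/37 gives 64.8-92.0.

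**4. Chance that the exact lower limit exceeds 80%.** This is P(X ≥ r) for X ~ Bin(n, p), where r is the smallest count whose lower limit exceeds 80%.

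| Events | r | true 85% | true 90% | true 92% |
|---|---|---|---|---|
| 46 | 43 (93.5%) | 7% | 31% | 49% |
| 94 | 83 (88.3%) | 23% | 77% | 93% |
| 140 | 122 (87.1%) | 28% | 89% | 98% |

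The 92% column is the BEA sensitivity that Section 2.0 plans to detect.

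**5. Specificity.** The shortfall concerns sensitivity. Among 330 women below 4% (Group A in Section 5), 330 − 46 = 284 would be event-free. At 80% specificity, 227/284 gives 74.8-84.4 (±4.8).

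**The case against.** The strongest defence is context. The sentence gives cumulative cases as its reason, follows the 6-month whole-cohort figures and introduces Analyses 1 to 4. The subgroup comparisons in Section 2.0 are not among those numbered analyses. Read this way it is loose wording that is correct for Analysis 2. This explains how it arose, but it says all subsequent analyses, and the document itself plans one with 46 events.

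A reader might infer more: that 46 to 140 events cannot support the >80% criterion. The documents do not bear this out. At the protocol's own 92%, 94 or 140 events clear 80% with probability 93% or 98%. Only the 46-event group is weak (49%), and even there the chance is 80% if true sensitivity is 95%. Nor does any section tie the criterion to a subgroup. It stands beside a pooled 18-month table with 352 cases, although that pool includes women already positive by 6 months.

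The derived counts are also open. The 94 belongs to the 4-10% group, not strictly to the 4-8.9% group. The background (Section 1.4) says women with 4-8% swelling supply 50-60% of later cases: 175-210 events if read against 350, or 70-84 if read against 140. It also says up to 40% do not progress by 2 years; with 40% not progressing, 0.60 × 460 = 276 would. At 90% sensitivity, 158/175 gives 84.9-94.2 (±4.7) and 248/276 gives 85.7-93.2 (±3.7). So a failure of ±5 in the middle group is likely on one reading and absent on another. The 46-event group does not depend on this.

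**Conclusion.** The point holds in limited form. The statement on larger numbers and ±5% is correct for the whole-cohort 18-month analysis and false for the group below 4%, on the protocol's own count of 46. There the half-width is about 12 points at 80% sensitivity, 10 at 89% and 7 at 96%, so ±5 fails throughout the range the protocol considers. If 37 events is the intended figure, the intervals are wider still.

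For the 4-10% group and for both groups together, the widths (about 5 to 9 points with 94 events, 4 to 7 with 140, over 95% to 80% sensitivity) rest on the assumption that all early cases remain positive. They narrow if more of the 350 cases are new events. These are secondary comparisons and the primary objective, incidence, is unaffected. The error is in a stated precision, and it falls in the group most relevant to early detection.

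**What to change.** In Section 5, Sample Size Calculation:
- Limit the larger-numbers and ±5% statements to whole-cohort Analyses 1 and 2, at the 90-95% sensitivities illustrated.
- Give the expected event counts and exact interval widths for the Section 2.0 prediction comparisons, with their assumptions, and make no ±5% claim for the group below 4%.

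In Section 2.0:
- Reconcile the 46 events with the 14% of 264 beside it.
- State the expected events in the 4-8.9% group.
- Say on which population the >80% sensitivity and specificity criterion is judged. Pooling all women without lymphoedema at 6 months is one option, not a required correction.

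The cost is a few sentences and a small table. No patients, visits or measurements are added. The stated precision becomes less favourable.
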